A single-center, phase IV, randomized, prospective study investigating the efficacy of various wound closure devices in reducing postoperative wound complications

Regulatory Sponsor: **[name]**

Co-Investigators: [name]
[name]

NYULMC Orthopaedic Surgery
Hospital of Joint Diseases
[name]
[name]

Study Product: Zipper wound closure device, Monocryl + Dermabond,
Polyester mesh + Dermabond

Protocol Number: s16-02020

NCT Number: NCT03134209

Version: 1/10/17

CONFIDENTIAL

This material is the property of the NYU School of Medicine and Langone Medical Center. Do not disclose or use except as authorized in writing by the study sponsor

Initial version: 12/15/16

List of Abbreviations

TJA- Total joint arthroplasty

CONFIDENTIAL

This material is the property of the NYU School of Medicine and Langone Medical Center. Do not disclose or use except as
authorized in writing by the study sponsor

Study Summary

Title	A single-center, phase IV, randomized, prospective study investigating the efficacy of various wound closure devices in reducing postoperative wound complications
Short Title	Assessing various wound closure techniques; RCT
Protocol Number	i16-02020
Phase	4
Methodology	Randomized, control
Study Duration	7 months
Study Center(s)	Single-center
Objectives	To determine the efficacy of the experimental wound closure device in regards to reducing wound complications and costs
Number of Subjects	200 subjects
Diagnosis and Main Inclusion Criteria	Patients who are undergoing joint arthroplasty
Study Product, Dose, Route, Regimen	Zipper surgical skin closure device applied to the most superficial layer of skin following a joint arthroplasty
Duration of administration	Applied one-time to close the wound following joint arthroplasty. This device will be applied for up to 2-3 weeks
Reference therapy	Experimental treatment will be compared to two groups: 1) Monocryl + Dermabond 2) Polyester mesh + Dermabond
Statistical Methodology	Odd ratios will be used to determine which wound closure device is at higher risk of developing a wound complication

CONFIDENTIAL

This material is the property of the NYU School of Medicine and Langone Medical Center. Do not disclose or use except as authorized in writing by the study sponsor

Introduction

1.1 Background

Today's healthcare climate continues to emphasize the need for high-quality of care while minimizing the financial burdens of the patient, hospital, and payer. This is particularly relevant in total joint arthroplasty (TJA) as payment models are shifting toward bundled, pay-for-performance episodes of care,[1, 2] and away from the current plan of payments for each separate service provided. Given that the demands for TJA are projected to increase substantially for decades to come,[3] it is imperative to identify potential factors that may improve clinical outcomes, so that ultimately, costs per episodes of care are minimized.

One such area of improvement involves gaining a better understanding of the optimal wound closure technique following TJA. Specifically, two measures, wound closure times and surgical outcomes, have been the focus of prior studies as they have been closely associated with avoidable healthcare expenditures. Common complications of failed wound closures include infection, dehiscence, edema, and arthrofibrosis.[4-15] Not only do these failures lead to exorbitant costs through poorer outcomes (i.e. delayed progress in physical therapy, increased length of stay, increased readmission, and reduced patient satisfaction), they are also known to have a significant impact on the overall long-term health of the patient.

The three common options for wound closure following TJA include sutures, staples, and skin adhesives. While conventional sutures and staples have been the mainstay techniques in TJA for some time, the barbed suture is a newer technique that has emerged as a popular option within the last decade. Reported advantages of this technique include the need for less material per incision, lower closure costs, shorter length of closure time, and a knotless application of the suture. [8-11, 16] Outcomes in regards to complications have been variable when compared to conventional sutures in TJA.[8-11] The skin adhesive that is most commonly used today includes a 2-octyl cyanoacrylate (OCA), high-viscosity, flexible glue.[7, 17] This technique has been associated with decreased wound closure times,[18] high satisfactory cosmetic results,[17, 19] and surgical outcomes comparable to conventional sutures.[17, 20] Other newer techniques such as the zipper technique[21] and variations of the OCA skin adhesives have also been sources of experimentation.

Wound closure techniques have been well-studied in a variety of surgical specialties, however, the level of evidence reported in the literature in regards to TJA is scarce. Thus, the current randomized, control trial study aims to investigate the perioperative outcomes and costs of various wound closure techniques including zipper technology, monocryl suture plus Dermabond, and polyester plus Dermabond wound closure techniques. The zipper wound technology is a new wound closure device that is an alternative to the commonly used conventional staples and sutures. The device acts like a scaffold to stabilize the adjacent sides of a wound in order to minimize forces that can disrupt normal healing of the skin. Monocryl suture plus Dermabond is a commonly used combination of wound closure techniques today. Finally, the polyester plus Dermabond closure techniques combines the OCA topical skin adhesive with a flexible, self-adhesive polyester mesh that has proven to reduce wound closure times and have a significant greater skin holding strength than skin staples or subcuticular sutures in one study. Although there have been prior studies measuring the efficacy of these closure techniques individually, none have compared these three particular ones following TJA. Furthermore, in order to provide the highest level of evidence as possible for the study, it will be conducted in a randomized fashion.

CONFIDENTIAL

This material is the property of the NYU School of Medicine and Langone Medical Center. Do not disclose or use except as authorized in writing by the study sponsor

The hypothesis of the study is that there will be reduced complications rates, improved outcomes, and overall cost reduction for the zipper technology versus the other two closure techniques.

1.3 Clinical Data to Date

A recent meta-analysis[22] compared this surgical zipper technique to conventional sutures in closing surgical wounds based on 4 randomized, control trials. The study showed that there was a similar incidence of postoperative complications, less time for incision closure, less cost for personnel involved in the procedure as well as total operating times, and higher levels of patient comfort for the zipper technique cohort.

Research Risks and Benefits

Risks

There are low associated risks with all three closure techniques. Commonly documented complications associated with all closure techniques include infection, abscess formation, hematoma formation, dehiscence, prolonged discharge, and allergic reactions. These risks are minimal overall with minimal risk differences between each technique. Thus, at worst, there will be minimal change in risks whether patients are randomized or have the option to choose a specific technique.

Benefits

There may be no direct benefit from agreeing to participate in this study. It is hoped that the knowledge gained will be of benefit to others in the future.

1.4 Primary and secondary objectives:

Primary objective: to identify the rate of complications associated with each type of wound closure technique. Some of these complications will include infection, abscess formation, dehiscence, prolonged drainage, allergic reactions, among others.

Secondary objective: to determine the cost effectiveness of each of these wound closure techniques, which will be calculated by the differences in supply costs, total lengths of operation, and postoperative complications.

CONFIDENTIAL

This material is the property of the NYU School of Medicine and Langone Medical Center. Do not disclose or use except as authorized in writing by the study sponsor

2 Study Design

2.1 General Design

A single-center, phase IV, randomized, prospective study. Patients will be expected to participate for about 4 months. Please refer to section 4 for a summary description of the sequence and duration of all trial periods including follow-up.

2.2 Primary Study Endpoints

Each complication will be documented for every patient. The rates of complication will be analyzed individually for each technique, and risk ratios will be conducted between techniques to determine which technique has the lowest risk of developing a complication. Complications include infection, abscess formation, dehiscence, prolonged drainage, allergic reactions, among others.

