3.2 Method for Assigning Subjects to Treatment Groups

Names of patients who are consented for the study will be inputted into a computer and randomized to one of the three treatment groups based on an alternating method. A randomized control trial will provide the highest level of evidence without altering the potential risks to the patient as all three wound closure techniques have been found to have comparable complication rates.

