5.1 Sample Size Determination

Based on an 80% power analysis, incidence rates reported from past studies, and a ratio of 1:1:1 cohort size between the different treatment groups involved, a total of 200 patients will be included in the study. Given an estimated 700 total hip and knee replacements done in a quarter each year at NYULMC, the project is scheduled to take a total of 7 months. It is estimated that 50% of all patients will be approached to be consented

from these 700 patients (a total of 350 patients will be enrolled to reach the target number of participants), and an estimated 60% of these patients will agree to follow through with the study.

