5.2 Statistical Methods

Data on patient baseline characteristics, procedural characteristics, perioperative outcomes, functional outcomes, and costs will be collected. Single variable and multivariate statistical analysis will be performed to assess the aforementioned data points. Dichotomous data outcomes will be analyzed using odd ratios and chi-squared tests while continuous data points will be analyzed using Student t-tests. Each complication will be documented for every patient. The rates of complication will be analyzed individually for each technique, and risk ratios will be conducted between techniques to determine which technique has the lowest risk of developing a complication. Complications include infection, abscess formation, dehiscence, prolonged drainage, allergic reactions, among others. Cost effectiveness will be determined by the differences in quality metrics such as LOS, readmissions, cost of supplies, and differences in wound closure time between the different wound closure techniques. Each of these variables will be calculated based on the associated hospital costs and analyzed to determine the most cost effective wound closure technique.

CONFIDENTIAL

This material is the property of the NYU School of Medicine and Langone Medical Center. Do not disclose or use except as authorized in writing by the study sponsor

6 Safety and Adverse Events

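### The plan names a lowest-risk technique from between-arm ratios with no interval, error rate or inconclusive outcome, and its chi-squared test is not tied to that conclusion

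*Combined protocol and SAP*

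**What the plan says.** Section 2.2 (Primary Study Endpoints) says the complication rate will be analysed for each technique, and then that "risk ratios will be conducted between techniques to determine which technique has the lowest risk of developing a complication". Section 5.2 (Statistical Methods) repeats the sentence. The Study Summary says that odds ratios will settle which device carries the higher risk.

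Section 5.2 also plans, two sentences before that statement, that "Dichotomous data outcomes will be analyzed using odd ratios and chi-squared tests". It does not say whether the test is overall or pairwise, at what level it is done, or whether it must be significant before a technique is named. No section mentions a confidence interval, a multiplicity rule, or what is reported if the arms cannot be separated.

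Section 5.1 gives the size: "a total of 200 patients will be included in the study", in a 1:1:1 ratio.

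On what to expect, the Introduction states "The hypothesis of the study is that there will be reduced complications rates" for the zipper against the other two techniques. Section 1.3 cites a meta-analysis of zipper against sutures in which "there was a similar incidence of postoperative complications". Section 3.2 says that "all three wound closure techniques have been found to have comparable complication rates".

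**The concern.** Unless arms tie, one of three observed rates is always the lowest. A rule that turns the ratios into a statement about which technique has the lowest risk therefore yields a winner from chance alone, and gives the reader no means of telling that winner from a real one. The test that could guard against this is planned, but nothing makes the conclusion depend on it.

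Complications are the primary endpoint, and section 1.4 also counts them in the cost-effectiveness calculation. A chance ranking would be the headline result and would carry into the cost comparison.

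**Working it through.** **Inputs.** Total 200, ratio 1:1:1 and 80% power (section 5.1): 200/3 = 66.7, so about 67 per arm. The plan refers to "incidence rates reported from past studies" but states no rate, effect size, significance level or sidedness, so the figure of 200 can be neither reproduced nor refuted. The complication rates below are assumptions, and 0.05 two-sided is assumed for any test.

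**1. Ranking alone, all arms truly equal at rate p.** Let b and F be the binomial probability and distribution function for n = 67. Then

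P(one arm has strictly the fewest events) = 3 × Σₓ b(x; 67, p) × [1 − F(x; 67, p)]².

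| True rate in all arms | 0.5% | 1% | 2% | 3% | 5% | 8% |
|---|---|---|---|---|---|---|
| Single lowest arm by chance | 18% | 39% | 60% | 69% | 76% | 81% |

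The low values at the left arise because ties are common when events are few. With arms of 67, 67 and 66 ranked on observed rates, the unequal denominators break most ties, and the figures at 1, 2, 3, 5 and 8% become 42, 72, 83, 90 and 93%.

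**2. The same situation with a test as gate.** If an overall three-arm chi-squared test at 0.05 must be significant first, the false-positive rate is 3.9% at a 3% rate, 4.4% at 5% and 4.7% at 8%, and about 2.4% at a 1% rate. If any one unadjusted pairwise test at 0.05 suffices, it is about 11-12% at rates of 5-20%.

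**3. Ranking alone, zipper truly worse.** With zipper rate p_z and both comparators at p_c,

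P(zipper uniquely lowest) = Σₓ b(x; 67, p_z) × [1 − F(x; 67, p_c)]²,

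and replacing 1 − F(x) by P(Y ≥ x) gives lowest or tied.

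| Zipper v comparators | Uniquely lowest | Lowest or tied |
|---|---|---|
| 5% v 3% | 9.1% | 22% |
| 8% v 5% | 8.1% | 16% |

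A tie names no winner, so the middle column is the relevant one.

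**4. What a null result would show.** Take 2/67 against 2/67, an observed rate of 0.0299 in each arm.

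- Wilson limits for one arm: 0.0082 to 0.1025.
- Newcombe half-width: √[(0.0299 − 0.0082)² + (0.1025 − 0.0299)²] = 0.076. The 95% interval for the difference is −7.6 to +7.6 points.
- Log risk-ratio standard error: √[2 × (1/2 − 1/67)] = 0.985. exp(±1.96 × 0.985) gives 0.15 to 6.9.

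Identical observed counts would leave a several-fold excess in either direction open.

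**The case against.** The strongest reply is that section 5.2 does plan a test. A complication is a dichotomous outcome, the chi-squared sentence stands in the same paragraph, and a fair reader may assume that it governs the ratios. This stands in part. A reader might infer that the trial will usually declare a false winner. The documents do not support that, because it follows only if the planned test is ignored. What they support is that the link is missing, and that the answer runs from about 4-5% to as much as 81% over the assumed rates, depending on a rule nobody has written.

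The chance-winner figures also depend on rates the plan does not give. At 1% or below a single lowest arm is the less likely outcome. The endpoint is broad and open-ended, which argues against very low rates, but section 1.3 calls the risks minimal, so the low end cannot be dismissed.

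A reader might further infer, from the statements on comparable rates in sections 1.3 and 3.2, that a null result will be reported as comparable safety and the devices then ranked on cost, so that a non-inferiority margin is missing. The documents do not support this. The stated hypothesis is that the zipper is better. The comparability statements serve as background and as justification for randomising. No section says how a null will be read or makes the cost analysis conditional on one. A superiority hypothesis needs no margin.

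**Conclusion.** The concern holds as a gap in the decision rule. The primary conclusion is worded as a ranking with no interval, no error rate and no inconclusive outcome, and the planned chi-squared test is not connected to it. Taken literally, at 67 per arm and equal true rates of 2% to 8%, the rule produces a single lowest technique by chance in 60% to 81% of trials (39% at 1%). With an overall test as gate it is about 4-5%. When the zipper is truly worse by the amounts assumed, the literal rule still names it alone as lowest in about 8-9% of trials.

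These sizes rest on assumed rates, an assumed 0.05 level and no dropout. The gap itself does not: it is visible in the text. The wide interval in step 4 is a reason to report a null as inconclusive; it is not evidence that the plan intends to claim equivalence.

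**What to change.** In sections 2.2 and 5.2, replace "risk ratios will be conducted between techniques to determine which technique has the lowest risk of developing a complication" with wording such as:

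> For each pair of techniques, the risk ratio and the risk difference (Newcombe or score method) are reported with 95% confidence intervals. One technique is stated to have lower risk than another only if the overall chi-squared (or exact) test across the three arms is significant at two-sided 0.05 and the 95% interval for that pair's risk difference excludes zero. Otherwise the comparison is reported as inconclusive, with its interval, and not as evidence of equal risk.

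Make the Study Summary sentence consistent with this. The decision rests on the risk difference because the risk ratio is undefined when the reference arm has no events. All three pairs are covered, including mesh against Monocryl, since the primary objective concerns every technique. With three arms, the overall test as gate holds the chance of any false statement of lower risk at about 5%. No comparability margin is needed.

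The cost is wording only: no added patients, visits or measurements. The downside is a less favourable likely conclusion. For example, with assumed rates of 10% v 5% and 67 per arm, the power of one pairwise test at 0.05 is Φ[(0.05 − 1.96 × √(2 × 0.075 × 0.925/67)) / √((0.10 × 0.90 + 0.05 × 0.95)/67)] = Φ(−0.865) = 19%, so inconclusive would be the usual report.

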2.3 Secondary Study Endpoints

Cost effectiveness will be determined by the increased LOS, readmissions, cost of supplies, and differences in wound closure time between the differences in wound closure techniques. Each of these variables will be calculated based on the associated hospital costs and analyzed to determine the most cost effective wound closure technique.

2.4 Inclusion Criteria

Following IRB approval, all patients who are scheduled for joint arthroplasty at NYULMC will be eligible to take part in this research study. Inclusion criteria includes:

- All patients ≥ 18 years of age treated with joint replacement surgery at our institution
- Patients who are willing to participate in post-operative surveys

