2.5 Exclusion Criteria

- Treatment of total joint replacement surgery at an outside institution
- Patients younger than 18
- Pregnant women, prisoners, adults unable to consent.

Vulnerable Subjects: No vulnerable subjects will be included within this study

CONFIDENTIAL

This material is the property of the NYU School of Medicine and Langone Medical Center. Do not disclose or use except as authorized in writing by the study sponsor

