3.1 Description

The zipper wound technology is a new wound closure device that is an alternative to the commonly used conventional staples and sutures. The device acts like a scaffold to stabilize the adjacent sides of a wound in order to minimize forces that can disrupt normal healing of the skin. The other treatment groups include monocryl + Dermabond (conventional sutures and skin adhesive glue) and polyester mesh + Dermabond. All products have been FDA approved.

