3.3 Preparation and Administration of Study Product

The three different treatment devices will be administered following the normal standard of care. All three wound closure devices are currently being used at NYULMC. No modifications to the normal standard of practice other than the randomization process will be implemented.

CONFIDENTIAL

This material is the property of the NYU School of Medicine and Langone Medical Center. Do not disclose or use except as authorized in writing by the study sponsor

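### Sections 2.4 and 2.5 do not require that a patient can receive all three closures, so a patient with a documented sensitivity to a study product is eligible and may be allocated to it

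*Combined protocol and SAP*

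**What the plan says.** Section 2.4 opens by stating that "all patients who are scheduled for joint arthroplasty at NYULMC will be eligible to take part in this research study". Its two listed criteria are "All patients ≥ 18 years of age treated with joint replacement surgery at our institution" and "Patients who are willing to participate in post-operative surveys". Section 2.5 excludes patients operated on elsewhere, those under 18, and "Pregnant women, prisoners, adults unable to consent". Neither section refers to allergy, sensitivity, contraindication, or suitability for each of the three closures.

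Other parts of the protocol bear on this:

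- The Risks text under Section 1.3 says: "Commonly documented complications associated with all closure techniques include infection, abscess formation, hematoma formation, dehiscence, prolonged discharge, and allergic reactions". That covers the zipper as well as the two comparators.
- Section 2.2 names allergic reactions among the complications that make up the primary endpoint, and Section 5.2 repeats this.
- Section 3.1 describes the comparators: "The other treatment groups include monocryl + Dermabond (conventional sutures and skin adhesive glue) and polyester mesh + Dermabond". Dermabond is therefore in two of the three arms.
- Section 3.3 says: "No modifications to the normal standard of practice other than the randomization process will be implemented".
- Section 4 states that the randomization determines which device is used at surgery. It gives no rule for overriding it.
- Section 5.1 specifies "a ratio of 1:1:1 cohort size between the different treatment groups involved" and a total of 200 patients.

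**The concern.** The protocol foresees allergic reactions and scores them as primary-endpoint events, but it does not screen for patients already known to be prone to them. In ordinary practice a surgeon can choose a closure that avoids a known sensitivity. Randomization is the one departure from ordinary practice, and it removes that choice.

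Two things are at stake.

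- **Safety.** A patient could be exposed to a product to which a reaction is already on record. The Risks text under Section 1.3 argues that randomization changes risk very little, and Section 3.2 that it leaves potential risks unaltered. Both rest on techniques that are comparable on average, and an average does not cover a patient with a known sensitivity to the allocated product.
- **Interpretation.** If the allocation is followed, a foreseeable reaction counts in the primary endpoint. If the unblinded surgeon overrides it, the groups no longer match the allocation, and Section 5.2 defines neither an analysis population nor a rule for crossovers.

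**Working it through.** **The plan's own figures.** Section 5.1 gives 80% power and 200 patients, but no event rates, effect size, significance level or sidedness, so 200 cannot be reproduced. The recruitment figures can be: 700 × 0.50 = 350 approached, and 350 × 0.60 = 210 expected to agree, which is enough for 200.

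**Step 1: chance of allocation to the product concerned.** With 1:1:1 allocation and Dermabond in two arms, P(Dermabond) = 2/3. For a product used in one arm only (zipper, Monocryl or polyester mesh), P = 1/3.

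**Step 2: how many patients.** The documents give no prevalence of known sensitivity, so s is an assumption. Expected glue-sensitive patients in the Dermabond arms = 200 × s × 2/3. The chance of at least one among about 133 such patients is 1 − (1 − s)^133. Both assume that none is filtered out informally before entry.

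- s = 1%: 200 × 0.01 × 2/3 = 1.3 patients; chance of at least one, 74%.
- s = 2%: 200 × 0.02 × 2/3 = 2.7 patients; chance of at least one, 93%.

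**Step 3: effect on the risk ratio.** Let p be the background complication rate (assumed) and r the probability that a sensitive patient reacts (set to 1, its maximum). Suppose there is no other difference between arms and no zipper sensitivity. Then:

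- comparator rate = p + (1 − p) × s × r
- zipper rate = p
- risk ratio = zipper rate / comparator rate

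For p = 5% and s = 1%: 0.05 + 0.95 × 0.01 = 0.0595, and 0.05/0.0595 = 0.84. For s = 2%: 0.05 + 0.95 × 0.02 = 0.069, and 0.05/0.069 = 0.73 (0.725 before rounding).

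| Background p | Sensitivity s | Comparator rate | Risk ratio | Chance of a significant pairwise result favouring zipper (nominal 2.5%) |
|---|---|---|---|---|
| 5% | 1% | 5.95% | 0.84 | 4.3% |
| 5% | 2% | 6.9% | 0.73 | 6.7% |
| 5% | 5% | 9.75% | 0.51 | 18.0% |
| 10% | 1% | 10.9% | 0.92 | 3.7% |
| 10% | 2% | 11.8% | 0.85 | 5.2% |
| 10% | 5% | 14.5% | 0.69 | 12.1% |

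The last column is the power of a two-proportion comparison at 200/3 = 66.7 patients per arm.

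**Step 4: dependence on the zipper assumption.** If sensitivity to the zipper is as common and as reactive as sensitivity to Dermabond, both rates equal p + (1 − p) × s × r and the risk ratio is 1.0. Section 1.3 lists allergic reactions for all techniques, so zero zipper sensitivity cannot be taken from the documents.

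**Step 5: recruitment after an exclusion.** Excluding 1% leaves 210 × 0.99 = 208; excluding 3% leaves 210 × 0.97 = 204. At 5% it would be 210 × 0.95 = 199.5, about the target.

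**The case against.** The strongest reply is that the protocol has informal safeguards. Under Section 2.6 surgeons identify the participants and discuss the study with them. The Section 4 visit table schedules a preoperative medical history. Devices are applied under the usual standard of care, and a patient who knows of an allergy can decline. This stands in part: the text permits entry of sensitive patients but does not show that any would enter. However, none of these safeguards is written as a screening or override rule, and the history is not tied to any eligibility decision.

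A second reply concerns bias. A reader might infer that sensitive patients will be allocated to glue, and that the trial is therefore biased towards the zipper, the technique that the protocol expects to do better. The documents do not support that. Dermabond sensitivity on its own would raise both comparator rates, but allergic reactions are listed for the zipper too, and no prevalence is given for any product. If the allocation is followed, the extra reactions are also a real treatment effect in a poorly chosen population, which is a question of applicability and not bias in the strict sense. Strict bias would come from steering or overriding, and its direction is unknown.

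A third reply concerns size, and it also stands. Even 3% glue sensitivity, with every sensitive patient reacting, adds about two events per comparator arm (66.7 × 0.03). One binomial standard deviation at a 5% rate is about √(67 × 0.05 × 0.95) = 1.8 events.

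**Conclusion.** The gap in the eligibility text is real and should be closed. As written, a patient with a documented sensitivity to a study product is eligible and may be allocated to it, with a 2/3 chance for Dermabond and 1/3 for a product used in one arm only. The resulting harm is avoidable and would count in the primary endpoint.

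The effect on the comparison is probably small and its direction is open. With a 5% background rate, 1% to 2% glue sensitivity, every sensitive patient reacting and no zipper sensitivity, the risk ratio is about 0.84 to 0.73. The chance of a spurious significant pairwise result is then roughly 4% to 7% against a nominal 2.5%. All four inputs are assumptions. Only at about 5% sensitivity does the distortion become large, and equal zipper sensitivity removes it. The case therefore rests mainly on avoidable harm and only secondarily on an endpoint with few events: about 66.7 × 0.05 = 3.3 per arm at a 5% rate.

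**What to change.** Reconcile the eligibility text with the allergy risk that the protocol itself lists. Add to Section 2.5 an objective exclusion for documented, known hypersensitivity to any component of the three study closures, with the clinical wording left to the investigators. Adjust the opening sentence of Section 2.4 so that it no longer makes every scheduled patient eligible. Check the criterion against the preoperative history already scheduled, and record it on the screening form before the allocation is made.

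Do not add a discretionary judgement by the surgeon that all three closures are acceptable. Section 3.2 assigns patients by an alternating method, so the next arm can be predicted, and a surgeon's veto would offer a sanctioned way to steer patients. A criterion that can be verified from the record does not have that weakness to the same degree.

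The cost is a line in Section 2.5, a small edit to Section 2.4 and one item on the screening form. A few patients are lost (210 expected consenters become about 208 to 204 if 1% to 3% are excluded), and the results will not apply to patients with known sensitivities.
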